14.1.5 Recording and Reporting Adverse Events

All AEs and SAEs will be recorded and reported from the signing of the informed consent form (ICF) to the time of the FU Visit. The Investigator must instruct the subject to report AEs and SAEs during this time period. Reports of death within 30 days after the last contact with the subject will be reported to the Sponsor and additional information relative to the cause of death will be sought and documented.

All AEs and SAEs must be recorded on source documents. All AEs and SAEs for subjects who receive a treatment assignment will be recorded in the eCRF.

The Investigator must follow-up as medically necessary on all AEs and SAEs until the events have subsided, the condition has returned to baseline, or in case of permanent impairment, until the condition stabilizes.

AEs should be based on the signs or symptoms detected during the physical examination and on clinical evaluation of the subject. In addition to the information obtained from those sources, the subject should be asked the following nonspecific question: "How have you been feeling since your last visit?" Signs and symptoms should be recorded using standard medical terminology.

Any unanticipated risks to the subjects must be reported promptly to the relevant ethics committee(s) and regulatory agency(ies).

14.1.6 Reporting of Pregnancies Occurring During the Study

Study center personnel must report every pregnancy from the time the subject signs the ICF through the FU Visit. Within 24 h of learning of the pregnancy, the study center personnel must report the event on the Clinical Trial Pregnancy Form and fax or email it to the SAE/Pregnancy fax number or email provided in [Section 14.1.4](#), even if no AE has occurred. Pregnancies in female partners of male subjects occurring during the time frame described above must also be reported.

The pregnancy must be followed to term and the outcome reported by completing the Clinical Trial Pregnancy Form. If the pregnancy is associated with an SAE (e.g., if the mother is hospitalized for hemorrhage), a separate SAE Form for Clinical Trials must be filed as described in [Section 14.1.4](#) with the appropriate serious criterion (e.g., hospitalization) indicated, in addition to the Clinical Trial Pregnancy Form.

14.2 CLINICAL ASSESSMENTS

Safety parameters will be monitored according to standard medical practice and guidelines for oral administration of study drug. Vital sign assessments (temperature, blood pressure, pulse, respiratory rate, and oxygen saturation), medical history, prior and concomitant medications, height, weight, and physical examination findings will be conducted at the specified time points outlined in the Schedule of Assessments and Procedures ([Table 3-1](#)) and [Section 11.0](#).

14.3 LABORATORY ASSESSMENTS

Blood samples for clinical laboratory tests and blood/urine samples for pregnancy tests will be collected at baseline and throughout the study according to the Schedule of Assessments and Procedures ([Table 3-1](#)) and [Section 11.0](#).

Unscheduled clinically-indicated laboratory tests (emergency or unscheduled tests) should be conducted at the local or regional laboratory on an as-needed basis.

14.4 DATA MONITORING COMMITTEE

An internal, blinded Data Monitoring Committee (DMC) will be utilized in this study. The DMC will perform periodic reviews of blinded data from the study to evaluate subject safety, compliance with the study protocol, and the quality of data. Safety of study drug will be monitored by reviewing AEs, SAEs, and the safety laboratory assessments on a regular basis. If specific issues are identified that warrant more extensive review, the DMC will recommend that experts external to the company review the data and provide a formal opinion of their significance and recommend any necessary interventions.

15.0 PHARMACOKINETIC EVALUATION

The PK data acquisition and analysis strategy entails the use of a sparse PK sampling schedule. Pharmacokinetic samples will be obtained from all subjects at sites where PK sampling is possible (for which a study center has been identified by the Sponsor as ineligible to perform PK assessments).

Pharmacokinetic sample handling and shipping procedures are described in the PK Sample Handling and Shipping Manual.

15.1 PHARMACOKINETIC BLOOD SAMPLE COLLECTION

Efforts will be made to obtain PK samples from all subjects on Day 3 and Day 4 at sites where PK sampling is possible, as described below. Blood samples for PK analyses will be collected at the following times:

- Day 3: Pre-dose sample will be collected within 10 minutes before administration of study drug
- Day 3: Post-dose at 2-4 h; subjects who have been hospitalized are also required to have a post-dose PK sample at 6-10 h
- Day 4: 24-28 h after the Day 3 dose.

Refer to the PK Manual for additional details regarding PK sample collection times and handling instructions.

15.2 PHARMACOKINETIC ANALYSES

Plasma samples from nafithromycin-treated subjects will be analyzed to determine concentrations of nafithromycin using a validated assay.

The PK Population in this study will include all subjects in the Safety Population who received at least 1 dose of oral nafithromycin and had at least 1 analyzable plasma PK sample ([Section 16.1.6](#)).

16.0 STATISTICAL METHODS

16.1 STUDY POPULATIONS

16.1.1 Safety Population

The safety population will include all randomized subjects who receive any amount of study drug (nafithromycin or moxifloxacin). Subjects will be analyzed according to the treatment actually received.

16.1.2 Intent-to-Treat Population (ITT)

The ITT population will include all subjects who were randomized.

16.1.3 Microbiological Intent-to-Treat Population (micro-ITT)

The micro-ITT population will include all ITT subjects who have at least one baseline Gram-positive or atypical bacterial pathogen known to cause CABP, including bacterial pathogens identified by respiratory specimen culture (e.g., respiratory fluid obtained by bronchoalveolar lavage or bronchoscopy; pleural fluid obtained by thoracentesis; or expectorated or induced sputum meeting adequacy criteria), blood culture, urinary antigen test (*S. pneumoniae*, *L. pneumophila*), or atypical bacterial serologic response (*M. pneumoniae*, *C. pneumoniae*, *L. pneumophila*). Subjects with sole baseline Gram-negative bacterial infection will be excluded from this population.

16.1.4 Clinically-Evaluable Population (CE)

The CE population will include all ITT subjects who follow important components of the trial. Sufficient information regarding the clinical course of CABP must be available to determine the subject's clinical outcome at TOC, and the subject must not have confounding factors that interfere with the assessment of that outcome.

In order to be included in the CE population, subjects must meet all of the following criteria:

- Meet the clinical disease criteria for CABP as described in Inclusion Criterion #3 (Inclusion Criteria 3a–3e; [Section 9.2](#))
- Receive at least 1 dose of study drug
- Do not receive non-study, potentially-effective, systemic antibacterial therapy between Day 1 and TOC (except in cases of treatment failure)
- Have an Investigator-determined clinical response of clinical cure or clinical failure at TOC (unless determined to be a prior clinical failure at EOT)
- Receive at least 80% of the intended doses of study drug therapy

- Receive at least 48 h of study drug therapy in order to be considered an evaluable clinical failure and at least 72 h of study drug therapy in order to be considered an evaluable clinical success

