9.7 GUIDANCE TO INVESTIGATORS ON WHEN TO END STUDY DRUG THERAPY

The duration of study drug in this study is a fixed 7-day course in all three Treatment Arms; therefore, subjects who are improving clinically will receive no less or no more than 7 days of the study treatment regimen. At Day 7 (EOT), an assessment of clinical outcome will be performed by the Investigator. A subject will be determined as a clinical cure at EOT if the subject is alive and the infection is sufficiently resolved such that further antibacterial therapy is not needed ([Section 13.2.2](#)). Note that subjects with CABP may have some residual findings related to infection (i.e., cough) requiring non-antibiotic ancillary treatment (e.g., expectorant) at EOT and still meet criteria for clinical cure.

If additional antibacterial therapy is required for the index CABP (e.g., progressively worsening CABP between Day 1 and Day 7, or gradually improving CABP that requires additional antibacterial therapy beyond 7 days), study drug should be discontinued, the subject will be deemed a clinical failure on the day of study drug discontinuation, and open-label antibacterial therapy will be started at the discretion of the Investigator. Administration of blinded study drug will not be allowed beyond Day 7. In cases of premature discontinuation of study drug, subjects should not be discontinued from the study itself; subjects should remain in the study and undergo all scheduled assessments at EOT, TOC and FU ([Section 11.0](#)).

The Investigator may use culture and susceptibility results from the local microbiology laboratory to help guide therapy; however, decisions to continue or discontinue study drug should be based on clinical response rather than susceptibility results (as nafithromycin susceptibility testing is not available at the local site). If the index CABP is caused by a microorganism that is not susceptible to fluoroquinolones, macrolides, or ketolides in vitro, the decision to continue or discontinue study treatment should be based on the subject's clinical course and the Investigator's clinical judgment. These cases should be discussed with the Medical Monitor prior to prematurely discontinuing study drug, and the rationale for this decision should be recorded in the source documents.

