13.0 EFFICACY EVALUATION

13.1 PRIMARY AND SECONDARY EFFICACY VARIABLES

Primary efficacy variable:

- Clinical response at Day 4 (ITT population)

Secondary efficacy variables:

- Clinical response at Day 4 (micro-ITT population)
- Clinical outcome at EOT and TOC (ITT and CE populations)
- Improvement in CABP symptoms and normalization of vital signs at Day 4 (ITT population)
- Clinical outcome at TOC (micro-ITT population)
- By-subject and by-pathogen microbiological response at TOC (micro-ITT and ME populations)
- Hospitalization prior to FU (ITT population)

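### One CE population, defined by evaluability at TOC, is also used at EOT, so some valid EOT cures are dropped because of events after EOT

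*Combined protocol and SAP*

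**What the plan says.** Section 13.1 lists as a secondary variable "Clinical outcome at EOT and TOC (ITT and CE populations"). The synopsis and Sections 7.2 and 13.2.2 use the same pairing. Only one CE definition exists, in Section 16.1.4, and it looks to TOC throughout: enough information "must be available to determine the subject's clinical outcome at TOC".

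Two of its criteria depend on what happens after EOT:

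- TOC outcome: "Have an Investigator-determined clinical response of clinical cure or clinical failure at TOC (unless determined to be a prior clinical failure at EOT".
- Outside antibacterials: "Do not receive non-study, potentially-effective, systemic antibacterial therapy between Day 1 and TOC (except in cases of treatment failure".

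Two further criteria bear on failures: "Receive at least 80% of the intended doses of study drug therapy" and "Receive at least 48 h of study drug therapy in order to be considered an evaluable clinical failure". The second goes on to set 72 h for an evaluable success. The list is cumulative: "In order to be included in the CE population, subjects must meet all of the following criteria".

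Two other rules decide how subjects reach TOC. Section 13.2.2 carries a failure forward to later visits. Section 9.4.2 makes a subject who withdraws without having failed indeterminate at every remaining assessment.

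**The concern.** Whether a subject's EOT result counts in CE should depend on what was known by EOT. Here it depends on the EOT outcome and on later data. Someone cured at EOT who then withdraws, misses TOC or is indeterminate there, or takes an antibacterial for an unrelated reason, is removed, although none of this alters the EOT cure. Someone who failed at EOT needs no TOC outcome to stay in.

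At stake are the CE cure rate at EOT, the number of evaluable subjects behind it, and the between-arm difference with its 95% CI, which Section 16.2.3.2 plans to tabulate. Section 16.2.1 says the data are meant to inform the design of Phase 3 studies, so a wrongly selected CE rate or attrition figure could be carried into that planning.

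**Working it through.** **1. The plan's own figure.** The documents give no expected CE cure rate at EOT. The only precision figure is in Section 16.2.1: 78% Day 4 response, 75 per arm, 95% CI 66.9% to 86.7%. Clopper-Pearson with x = 0.78 × 75 = 58.5 gives 66.94% to 86.75%, which agrees. It supplies the n per arm and a sense of scale, nothing more.

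**2. Effect of the post-EOT criteria alone.** Let p be the true EOT cure rate, m the share of EOT cures lost for post-EOT reasons, and suppose no failure is removed. Then

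CE rate at EOT = p(1 − m) / [p(1 − m) + (1 − p)].

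Both p and m are assumptions.

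| p | m = 5% | m = 10% | m = 15% |
|---|---|---|---|
| 80% | 0.76/0.96 = 79.2% (−0.8) | 0.72/0.92 = 78.3% (−1.7) | 0.68/0.88 = 77.3% (−2.7) |
| 90% | 0.855/0.955 = 89.5% (−0.5) | 0.81/0.91 = 89.0% (−1.0) | 0.765/0.865 = 88.4% (−1.6) |

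**3. Results lost.** At p = 90% and 75 per arm: 75 × 0.9 × 0.05 = 3.4 to 75 × 0.9 × 0.15 = 10.1 subjects, or about 3 to 10.

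**4. Between-arm difference.** With equal true rates and m = 5% in one arm and 15% in the other, the spurious difference is 79.2 − 77.3 = 1.9 points at p = 80% and 89.5 − 88.4 = 1.1 points at p = 90%.

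**5. Adding the criteria that can remove failures.** Section 9.7 states: "The duration of study drug in this study is a fixed 7-day course in all three Treatment Arms". If intended doses means all seven (assumption), 0.8 × 7 = 5.6, so six doses are needed. A failure stopped after five doses has 5/7 = 71% and leaves CE. Let f be the share of EOT failures removed:

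CE rate at EOT = p(1 − m) / [p(1 − m) + (1 − p)(1 − f)].

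The bias is zero when f = m, downward when f < m and upward when f > m. At p = 85%, m = 10%:

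- f = 0: 83.6% (−1.4)
- f = 10%: 85.0% (0)
- f = 25%: 87.2% (+2.2)
- f = 50%: 91.1% (+6.1)

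**6. In counts.** Take 75 subjects with 64 EOT cures and 11 EOT failures: 64/75 = 85.3% (95% CI 75.3 to 92.4). Losing 6 cures gives 58/69 = 84.1% (−1.3). Removing 1 failure as well gives 58/68 = 85.3%, which cancels the shift. Removing 5 gives 58/64 = 90.6% (+5.3).

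**7. Repairing only one side.** At p = 85% and f = 25%, setting m = 0 while still counting against seven doses gives 0.85/(0.85 + 0.15 × 0.75) = 88.3%, further from 85% than the 87.2% in step 5. The dose criterion has to be settled together with the TOC criterion.

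**The case against.** A reader might infer that EOT failures always remain in CE and that the CE cure rate at EOT is therefore biased downward. The documents do not support that. Failures are exempt from the TOC-outcome criterion, and the antibacterial criterion makes an exception for treatment failure, but every other criterion still applies to them. The dose criterion has no exception for failures. Sections 9.4.1 and 9.7 show failure commonly arising with study drug being stopped, so failures are the group most exposed to it. As steps 5 and 6 show, a modest loss of failures cancels or reverses the downward shift.

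The case for low importance is also fair. This is a secondary endpoint in a study that Section 16.2 calls exploratory, with no formal comparisons. ITT at EOT is reported alongside and has no such selection. A shift of 0.5 to 2.7 points is small beside a 95% CI half-width of roughly 7 to 10 points at 75 per arm. The documents give no basis for the 5% to 15% loss. Unequal loss by arm is speculative when treatment is double-blind, with placebo filling out seven days in the nafithromycin arms. A single set also has the merit that EOT and TOC are reported on the same subjects.

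Finally, Sections 16.2 and 16.4 announce a SAP whose text was not supplied, so whether it already splits CE by visit cannot be checked.

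These points limit the size and leave the sign open. They do not remove the defect: the selection comes from a rule Section 16.1.4 states, not from a detail left for later. The ITT result does not repair the CE estimate, and two opposing selections cannot be relied on to cancel.

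**Conclusion.** The point holds in this form: a CE set built for TOC is applied at EOT, where it discards valid EOT cures for reasons that arise afterwards and exempts EOT failures from the TOC-outcome requirement. The 0.5 to 2.7 point reduction and the 3 to 10 lost results per arm describe that selection in isolation and rest on the assumed loss and cure rates. They do not predict the net bias, whose direction the documents leave open. That also depends on how many failures the dose and 48 h criteria remove, and the protocol does not say how intended doses are counted for a subject stopped for failure. Counted against seven doses, the 80% criterion makes the 48 h minimum for a failure redundant, so those two lines need reconciling. This is a worthwhile, inexpensive improvement to a secondary analysis, with no bearing on the primary endpoint.

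**What to change.** Before database lock, define two evaluable sets in Section 16.1.4 or the SAP:

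- **CE-EOT**, for the EOT endpoint: investigator cure or failure at EOT; no confounding non-study antibacterial through EOT; and the disease, at-least-one-dose, 48 h/72 h and dose-compliance criteria kept.
- **CE-TOC**, for TOC: the present criteria. ME continues to be built on this set, since it is analysed only at TOC.

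In both sets, reconcile the 80% line with the 48 h minimum by counting intended doses up to the day of failure for subjects who fail, so that failures are not selectively removed. This concerns who is counted in the analysis and changes nothing in treatment.

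The cost is one extra population flag and no new data. The EOT and TOC CE analyses will no longer contain exactly the same subjects, so each table should state its own denominator.

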16.1.5 Microbiologically-Evaluable Population (ME)

The ME population will include all subjects who meet both micro-ITT population ([Section 16.1.3](#)) and CE population ([Section 16.1.4](#)) criteria.

16.1.6 Pharmacokinetic Population

The PK Population includes all subjects in the Safety Population who received at least 1 dose of oral nafithromycin and had at least 1 analyzable plasma PK sample.

16.2 METHODS OF ANALYSIS

This is an exploratory study and, therefore, is not powered for inferential statistical analyses and no formal comparisons between the treatment groups will be conducted.

All data will be summarized separately by study drug (nafithromycin for 3 days, nafithromycin for 5 days, and moxifloxacin). Descriptive statistics (mean, standard deviation, median, minimum, and maximum) will be presented for continuous variables for each study drug. Frequency distributions (counts and percentages) will be presented for categorical variables.

A comprehensive Statistical Analysis Plan will be prepared and finalized prior to database lock.

16.2.1 Determination of Sample Size

Approximately 225 adult subjects with CABP will be enrolled in this study. Randomization will have a 1:1:1 (Arm A: Arm B: Arm C) allocation ratio; therefore, approximately 150 subjects will be randomized to receive active oral nafithromycin. The objectives of this Phase 2 study are to collect initial efficacy data and to evaluate the safety and PK of oral nafithromycin in subjects with CABP. The sample size chosen for this study is considered to be adequate to achieve the study objectives and provide sufficient data to inform the design of future definitive studies, including Phase 3 studies, of nafithromycin. Assuming a 78% clinical response rate at Day 4 in the oral nafithromycin treatment arms, the sample size of 75 subjects per treatment arm will yield a 95% confidence interval around the response rate of 66.9% to 86.7%.

16.2.2 Analysis of Disposition and Subject Characteristics

Subject disposition (enrolment, discontinuations from the study), study drug administered, premature discontinuations from study medication, withdrawals from the study, and major protocol deviations will be summarized by treatment group in the ITT Population.

Demographics and baseline characteristics such as age, sex, race, weight, and medical history will be summarized by treatment group in the ITT using means, standard deviations, medians, minima and maxima for continuous variables, and counts and percentages for categorical variables.

16.2.3 Efficacy Analyses

16.2.3.1 Primary Efficacy Analysis

The primary efficacy evaluation will be the by-subject clinical response at Day 4 in the ITT population. Each subject will be classified programmatically as a responder, non-responder, or indeterminate based on CABP symptom data entered in the e-CRF ([Section 13.2.1](#)).

The number and percentage of subjects in each treatment group classified programmatically as a responder, non-responder and indeterminate will be reported. Exact 95% confidence intervals around the percentage of subjects classified as responders will be calculated for each treatment group using the Clopper-Pearson Method. The treatment difference will also be determined and a 95% confidence for the difference will be calculated using the method of Miettinen-Nurminen. Individual subject data will also be displayed as a listing.

